6.4. Subset Analyses

Subgroup analyses, based on baseline SARS-Cov-2 infection status (based on N-binding antibody results at Visit 1 before vaccination and medical history of SARS-CoV-2), will be performed on secondary immunogenicity endpoints by study intervention group with a BNT162b2 dose, as supplemental analyses.

6.5. Baseline and Other Summaries and Analyses

6.5.1. Baseline Summaries

6.5.1.1. Demographic Characteristics and Medical History

Descriptive summary statistics for demographic characteristics (age at vaccination, sex, race, ethnicity, and racial designation) and baseline SARS-CoV-2 infection status (based on N-binding antibody results at Visit 1 before vaccination and medical history of SARS-CoV-2) will be generated by study intervention group and for all participants in total, for participants 18 through 64 years of age and ≥65 years of age separately and combined, based on the safety population.

Each reported medical history term will be mapped to a SOC and PT according to MedDRA. The number and percentage of participants with an assigned vaccine having at least 1 diagnosis, overall and at each SOC and PT level, will be summarized by study intervention group and for all participants in total, for participants 18 through 64 years of age and ≥65 years of age separately and combined, based on the safety population.

6.5.2. Study Conduct and Participant Disposition

6.5.2.1. Participant Disposition

All participants in the mITT population will be included in the disposition summaries. Summaries will be displayed by study intervention, for participants 18 through 64 years of age and \geq 65 years of age separately and combined.

The number and percentage of randomized participants will be included in the participant disposition summary. In addition, the number and percentage of participants who received vaccinations, completed the follow-up visits, and withdrew before each follow-up visit phase, along with the reasons for withdrawal, will be tabulated by study intervention group and for the total sample for each age group separately and combined. The reasons for withdrawal will be those as specified in the database.

Participants excluded from each analysis population will also be summarized separately by study intervention group and age group separately and combined, along with the reasons for exclusion.

A listing of protocol deviations may also be provided.

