10.11.4. Substudy A Design

10.11.4.1. Overall Design for Substudy A

This is a Phase 1 randomized, open-label substudy to describe the safety and immunogenicity of up to 3 dose-level combinations of qIRV/bivalent BNT162b2 (original/Omi BA.4/BA.5). Bivalent BNT162b2 (original/Omi BA.4/BA.5) used was recommended by ACIP in 2022-2023. Approximately 360 participants will be enrolled across 2 age strata: approximately 180 participants 18 through 64 years of age and approximately 180 participants ≥65 years of age. Participants in each stratum will be randomized equally (30 participants per group) to each group to receive a dose of either:

- qIRV/bivalent BNT162b2 (original*/Omi BA.4/BA.5), at 1 of the 3 dose-level combinations shown in Table 1,
- CCI μg qIRV,
- μg qIRV, or
- µg Bivalent BNT162b2 (original/Omi BA.4/BA.5) administered concurrently in the opposite arm to licensed QIV.
- * Original refers to the ancestral strain (Wuhan-Hu-1; USA-WA1/2020), also referred to in this protocol as the reference strain.

Enrollment into each of the 2 age strata (18 through 64 and ≥65 years of age) may occur independently.

Safety and immunogenicity data from studies previously conducted in participants of a similar age range having received 1 dose of BNT162b2 at a dose level of µg and µg may be used as a control during the substudy analysis.

Enrollment in each age stratum will be controlled such that no more than 10 participants (considered the sentinel participants) can be vaccinated on the first day, vaccination of the remaining participants will commence no sooner than 24 hours after the tenth participant received his or her vaccination.

Stopping rules will apply to groups receiving combination bivalent BNT162b2 (original/Omi BA.4/BA.5) and qIRV as detailed in Section 10.11.8.6.

All participants will be asked to complete a reactogenicity e-diary for 7 days following each vaccination. Blood samples of approximately 50 mL will be collected for immunogenicity assessments prior to Vaccination 1 and at 1, 4, and 8 weeks after vaccination. All participants will be asked to provide an additional blood sample of approximately 2.5 mL at time points specified in Section 10.11.1 for assessment of troponin I.

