4. ANALYSIS SETS (POPULATIONS FOR ANALYSIS)

Data for all participants will be assessed to determine if participants meet the criteria for inclusion in each analysis population prior to unblinding and releasing the database, and classifications will be documented per standard operating procedures.

Population	Description
Screened	All participants who sign the ICD.
Randomized	All participants who are assigned a randomization number in
	the IWR system.
Evaluable immunogenicity	All participants who are eligible, receive the study
	intervention to which they were randomized, have blood
	drawn for assay testing within the specified time frame
	(26-35 days after vaccination), have at least 1 valid and
	determinate assay result at the 4-week postvaccination visit,
	and have no major protocol violations.

Population	Description
mITT	All randomized participants who receive the study
	intervention and have at least 1 valid and determinate assay
	result after vaccination.
Safety	All participants who receive the study intervention.

Major protocol deviations will be determined by clinical review. A major protocol deviation is a protocol deviation that, in the opinion of the sponsor's study medical monitor, would materially affect assessment of immunogenicity or efficacy, eg, participant receipt of a prohibited vaccine or medication/treatment that might affect immune response or a medication error with suspected decrease in potency of the vaccine. The sponsor's medical monitor will identify those participants with protocol deviations before any analysis is carried out.

The APE field will be included in the PIPD form from the CORD system and is used to help identify protocol deviations that may exclude participants from a particular population. For each reporting event, the most current endorsed version of the PIPD list must be used to generate the protocol deviation data set for analysis and reporting.

The APE flags for this study are as follows:

YES-POP1 (participants excluded from the safety population)
YES-POP2 (participants excluded from the evaluable immunogenicity population)
YES-POP4 (participants identified as having multiple enrollments at different sites)

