6.4.3. Study Conduct and Participant Disposition

6.4.3.1. Participant Disposition

All randomized participants will be included in the disposition summaries. Summaries will be displayed by study intervention group for participants 18 through 64 years of age.

The number of randomized participants will be included in the participant disposition summary. In addition, the number and percentage of participants who received vaccinations, completed the follow-up visits, and withdrew from the study, along with the reasons for withdrawal, will be tabulated by study intervention group.

Participants excluded from each analysis population will also be summarized by study intervention group and age stratum separately along with the reasons for exclusion (eg, for the evaluable immunogenicity population).

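### The Substudy A SAP bases disposition on the mITT population, so unvaccinated participants and those who leave before the first usable postvaccination sample drop out of the withdrawal summary

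*SAP*

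**What the plan says.** The first sentence of Section 6.5.2.1 of the Substudy A SAP sets the base: "All participants in the mITT population will be included in the disposition summaries". The next paragraph describes the content of the table. It begins "The number and percentage of randomized participants will be included in the participant disposition summary" and goes on to ask for those vaccinated, those who completed the follow-up visits, and those who "withdrew before each follow-up visit phase, along with the reasons for withdrawal, will be tabulated by study intervention group". A third paragraph adds a separate tabulation: "Participants excluded from each analysis population will also be summarized separately by study intervention group", with the reasons for exclusion.

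Section 4 of the same SAP defines mITT in two parts: "All randomized participants who receive the study" "intervention and have at least 1 valid and determinate assay" result after vaccination. It defines a separate randomized population that requires only a randomization number, and it places randomized but unvaccinated participants in that population.

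Protocol Section 10.11.4.1 sets the immunogenicity sampling times: "prior to Vaccination 1 and at 1, 4, and 8 weeks after vaccination".

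For the same table, Section 6.4.3.1 of the Substudy B SAP says: "All randomized participants will be included in the disposition summaries".

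**The concern.** A disposition table follows everyone who was randomized and shows where, when and why they were lost. A base defined by vaccination and a later laboratory result selects on the outcomes that the table is meant to report. Two kinds of participant are removed by rule: those never vaccinated, and those who left before giving a usable postvaccination sample.

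This matters in Substudy A because its primary objective is safety and tolerability. The interval before the first postvaccination sample largely coincides with the 7-day reactogenicity period. Protocol Section 7.2 lists reactogenicity events and AEs as separate reasons for leaving the study. A participant who stops in that week because the vaccine was poorly tolerated is one whose timing and reason the table most needs to show, and the stated base leaves that participant out.

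**Working it through.** The plan states no figure to reproduce. The check compares the sections and then illustrates the effect with simple proportions.

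**Who can be in mITT**

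1. Substudy A SAP, Section 4: membership requires randomization, vaccination and at least one valid postvaccination assay result.
2. Protocol Section 10.11.1: the first postvaccination immunogenicity sample is at Visit 3, 6 to 8 days after Visit 1. Visit 2, at 2 to 4 days, has no immunogenicity sample.
3. Three kinds of participant therefore fall outside mITT: those never vaccinated; those who leave before the Visit 3 sample; and those whose Visit 3 sample is missing or indeterminate and who leave before Visit 4.

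**What this does to the rows in Section 6.5.2.1**

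| Row requested | On the mITT base | On the randomized base |
|---|---|---|
| Randomized | 100% by definition | the actual denominator |
| Vaccinated | 100% by definition | informative |
| Withdrew before the 1-week sample | zero by construction | informative |
| Withdrew later | counted over a reduced denominator | counted over all randomized |

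**Illustration 1: early withdrawals only.** Assume 30 randomized in a group (Substudy A SAP, Section 2.3), k of whom are vaccinated and leave before the 1-week sample, with no other withdrawals and a valid result for everyone else. The randomized base gives k/30; the mITT base gives 0/(30 − k).

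| k (assumed) | Randomized base | mITT base |
|---|---|---|
| 1 | 1/30 = 3.3% | 0/29 = 0% |
| 2 | 2/30 = 6.7% | 0/28 = 0% |
| 3 | 3/30 = 10.0% | 0/27 = 0% |

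**Illustration 2: mixed losses.** Assume that, of 30 randomized, 1 is never vaccinated, 1 is vaccinated and leaves before the 1-week sample, and 1 leaves after week 4.

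- mITT base: N = 30 − 2 = 28; vaccinated 28/28 = 100%; withdrawn after vaccination 1/28 = 3.6%.
- Randomized base: vaccinated 29/30 = 96.7%; withdrawn after vaccination 2/30 = 6.7%; with the unvaccinated participant also counted as lost, 3/30 = 10.0%.

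**Substudy total.** About 360 participants are to be randomized. If 1% to 5% had no postvaccination assay result (an assumed range), 0.01 × 360 = 3.6 to 0.05 × 360 = 18 participants, so about 4 to 18, would be outside the table.

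**The case against.** The strongest reply is that Section 6.5.2.1 does not clearly plan to drop anyone. Its first sentence says mITT participants are included, not that only they are, and its next paragraph asks for randomized and vaccinated counts, which are pointless on an mITT base. That is fair as far as it goes: the section contradicts itself. But a programmer who follows the sentence that names the population would use the wrong base.

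The second reply is that the same people appear elsewhere in the Substudy A SAP:

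- The third paragraph of Section 6.5.2.1 summarizes exclusions from each population, with reasons.
- Section 6.5.3.1 tabulates vaccination for all randomized participants.
- Section 6.5.2.2 tabulates blood samples among randomized participants.
- Section 6.1.2.2 summarizes AEs leading to withdrawal in the safety population.
- Section 6.1.1.1 keeps reactogenicity data collected from participants who discontinue.

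This stands, and it limits the loss to the withdrawal tabulation. It does not close the gap. A reason for exclusion from a population is not a withdrawal date and reason. The AE summary covers only vaccinated participants who left because of an AE. It would miss participants lost to follow-up and those who left at their own request, and it may miss withdrawals coded as reactogenicity events.

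Third, the numbers may be small. Randomization and vaccination are steps of the same visit (Protocol Section 10.11.8.8.2), and the first postvaccination immunogenicity sample follows 6 to 8 days later. The documents give no early-loss rate, so the illustrations show how the error works, not how large it will be. Fourth, Substudy A is descriptive and no primary or secondary estimate uses this table. Both points are correct and bear on importance, not on whether the base is wrong.

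**Conclusion.** The concern holds. As written, the base for disposition in the Substudy A SAP excludes unvaccinated participants and those who leave before a usable postvaccination sample. It makes the vaccinated and earliest-withdrawal rows uninformative, and it conflicts with the content requested in the same section. The conclusion rests on taking the first sentence of Section 6.5.2.1 as the operative population and on the mITT definition in Section 4.

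Each omitted participant is 1/30 = 3.3 percentage points of a group. The number omitted cannot be derived from the documents. The effect is confined to a study-conduct table, but attrition in that table would be understated whenever early losses occur. The SAP gives no reason for using mITT here, and its neighboring blood-sample and exposure tables use randomized participants.

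**What to change.** In Section 6.5.2.1 of the Substudy A SAP, replace the mITT population with all randomized participants as the base for the disposition summaries, matching Section 6.4.3.1 of the Substudy B SAP. Keep the separate summary of exclusions from each analysis population as it is. The change is one phrase, needs no additional data and removes the conflict within the section. If disposition tables have already been produced on the mITT base, rerun them on the randomized base.

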6.5.2.2. Blood Samples for Assay

For each blood sampling time point, the number and percentage of randomized participants providing blood samples within the protocol-specified time frame, as well as before and after the protocol-specified time frame, will be tabulated separately by study intervention group and for the total population, for participants 18 through 64 years of age and ≥65 years of age separately.

6.5.2.3. E-Diaries

The participants who were vaccinated and who transmitted and completed e-diaries will be summarized according to the vaccine actually received, for participants 18 through 64 years of age and ≥65 years of age separately and combined. Besides the analysis described in Section 3.4.2, the summary will also include the number and percentage of vaccinated participants not transmitting the e-diary, transmitting the e-diary, and completing the e-diary for any day in the required reporting period, by assigned study intervention and age group.

The number and percentage of participants transmitting and completing the e-diary for each day in the required reporting period, and overall, will be tabulated for each study intervention group and for the total sample, for participants 18 through 64 years of age and ≥65 years of age separately and combined.

The safety population will be used.

6.5.3. Study Intervention Exposure

6.5.3.1. Vaccination Timing and Administration

The number and percentage of participants randomized and receiving each study intervention will be tabulated for each study intervention group and overall, for all randomized participants 18 through 64 years of age and \geq 65 years of age separately and combined. The denominator for the percentages is the total number of participants in the given study intervention group or overall, for each age group. In addition, the relation of the randomized study intervention to the actual study intervention received will be presented as a cross-tabulation of the actual study intervention received versus the randomized study intervention, for participants 18 through 64 years of age and \geq 65 years of age separately and combined.

A listing of participants showing the randomized study intervention and the study intervention actually received will be presented.

6.5.4. Concomitant Medications and Nondrug Treatments

Each prior/concomitant vaccine will be summarized according to the ATC fourth-level classification. The prior/concomitant vaccine received before vaccination will be listed. The number and percentage of randomized participants receiving each vaccine after study intervention administration will be tabulated according to the assigned study intervention, for participants 18 through 64 years of age and ≥65 years of age separately and combined.

6.6. Safety Summaries and Analyses

6.6.1. Adverse Events

Local reaction, systemic event, AE, and SAE summaries, clinical safety laboratory assessments (troponin I), and ECG summaries and analyses are described under Primary Endpoints (Section 6.1).

A listing will be generated for all of the participants with unscheduled/unplanned visits because of severe (Grade 3) and Grade 4 reactions.

Descriptive summaries and listings of participants reporting immediate AEs during the protocol-specified ≥30-minute observation period for any acute reactions will be presented by study intervention group, for participants 18 through 64 years of age and ≥65 years of age separately and combined.

In addition, any symptom(s) that might be indicative of myocarditis or pericarditis within 4 weeks after a study vaccination (ECG, troponin level, cardiac echocardiogram, and/or cardiac magnetic resonance study) will be listed and/or summarized by study intervention group, for participants 18 through 64 years of age and ≥65 years of age separately and combined.

6.6.2. Laboratory Data

Clinical safety laboratory assessment (troponin I) is described under Primary Endpoints.

6.6.3. Vital Signs

A descriptive summary based on the safety population will be provided in accordance with the Pfizer reporting standards, and listings may be generated, for participants 18 through 64 years of age and >65 years of age separately and combined.

6.6.4. Electrocardiograms

The ECG summaries and analyses are described under Primary Endpoints.

7. INTERIM ANALYSES

7.1. Introduction

This study will use an IRC, an internal Pfizer committee that will review data to allow dose escalation or changes to continuation of specific groups. The IRC is independent of the study team and includes only internal members. The IRC charter describes the role of the IRC in more detail.

7.2. Interim Analyses and Summaries

No formal interim analysis will be conducted for this study. As the study is open label to the sponsor, the sponsor will conduct unblinded reviews of the data during the course of the study for the purpose of safety assessment, dose selection, and/or supporting clinical development.

1. VERSION HISTORY

Table 1. Summary of Changes

Version/	Associated	Rationale	Specific Changes
Date	Protocol		
2	Amendment 6	To motob mustocal	Undeted venious sections to name ve
2 22 Feb 2024	O9 Feb 2024	To match protocol amendment 6.	Updated various sections to remove references to objectives/endpoints/analyses related to participants 65+ years of age, removed references to initial enrollment groups and expanded enrollment groups throughout, and made the study design section (including the number of participants) consistent with the protocol amendment.
			Added an additional exploratory objective related to troponin and ECG abnormalities.
			Excluded the endpoint of achieving HAI seroconversion for all strains and HAI titers ≥1:40 for all strains.
			Removed references to "first vaccination," "first dose," and "each dose," since only 1 visit in protocol amendment 6 includes vaccination.
			Removed the 6-month serology secondary endpoint to be consistent with the protocol amendment and made the endpoint wording more consistent with protocol amendment.
		To respond to regulatory feedback.	Provided adjustment on the reporting of reactogenicity, taking into account the occurrence of AEs corresponding to reactogenicity terms within the 7-day reporting period after vaccination.
			Added GMR and the difference in seroconversion/seroresponse as supplementary analyses.
		To reflect updates in the team decision.	Added an analysis of seroconversion by baseline status.
1 27 Jun 2023	Amendment 4 16 Apr 2023	N/A	N/A

2. INTRODUCTION

This SAP provides the detailed methodology for summary and statistical analyses of the data collected in C5261001 – Substudy B. This document may modify the plans outlined in the protocol; however, any major modifications of the primary endpoint definition or its analysis will also be reflected in a protocol amendment.

2.1. Modifications to the Analysis Plan Described in the Protocol

Not applicable.

2.2. Study Objectives, Estimands, and Endpoints

The primary, secondary, and tertiary/exploratory objectives, associated estimands, and associated endpoints are described in the following table:

Substudy B (Phase 1/2)

	Substituty B (Fliase 1/2)				
Type	Objectives	Estimands	Endpoints		
	Primary Safety	Primary Safety	Primary Safety		
Safety	To describe the safety and tolerability of each study intervention in participants 18 through 64 years of age.	 In participants 18 through 64 years of age receiving at least 1 dose of study intervention, the percentage of participants with: Abnormal troponin I laboratory values 2 days and 1 week after vaccination. 	parameters detailed in Section 3.1.3.		
		 In participants 18 through 64 years of age receiving at least 1 dose of study intervention, the percentage of participants with: New ECG abnormalities 2 days and 1 week after vaccination. 	ECG abnormalities consistent with probable or possible myocarditis or pericarditis, as defined in the protocol.		
		 In participants 18 through 64 years of age receiving at least 1 dose of study intervention, the percentage of participants reporting: Local reactions for up to 7 days following vaccination in the right arm only. Systemic events for up to 7 days following vaccination. AEs from vaccination through 4 weeks after vaccination. SAEs from vaccination through 6 months after vaccination. 	(pain at the injection site, redness, and swelling) in the right arm only.		

Substudy B (Phase 1/2)

Type	Objectives	Estimands	Endpoints
Immunogenicity	Secondary	Secondary	Secondary
	•	1	•
	Immunogenicity ^a To describe the immune responses to SARS-CoV-2 and influenza elicited by each study intervention.	 Immunogenicity In participants 18 through 64 years of age complying with the key protocol criteria (evaluable participants): GMTs before vaccination and at each blood sampling time point after influenza vaccination. GMFR from before vaccination to each blood sampling time point after influenza vaccination. The proportion of participants achieving HAI seroconversion for each strain at each blood sampling time point after influenza vaccination. The percentage of participants with HAI titers ≥1:40 for each strain before vaccination and at each blood sampling time point after influenza vaccination. In participants 18 through 64 years of age complying with key protocol criteria (evaluable participants): GMTs before vaccination and at each blood sampling time point after vaccination for each strain. 	HAI titers for the matched seasonal strains recommended by WHO.
		 GMFR from before SARS-CoV-2 vaccination to each blood sampling time point after vaccination for each strain. Percentages of participants with seroresponse^c at each blood sampling time point after SARS-CoV-2 vaccination for each strain. 	
	Tertiary/Exploratory	Tertiary/Exploratory	Tertiary/Exploratory
	To describe the immune response to emergent variants (under monitoring, of interest, and/or of concern) in participants 18 through 64 years of age.	As detailed in the SAP (Section 3).	SARS-CoV-2— neutralizing titers for variants (under monitoring, of interest, and/or of concern).

	Substudy B (Phase 1/2)				
Type	Objectives	Estimands	Endpoints		
	To describe the troponin and ECG abnormalities detected in participants who are evaluated for possible cardiac symptoms.	As detailed in the SAP (Section 3).	 Troponin I laboratory parameters as detailed in the protocol. ECG abnormalities consistent with probable or possible myocarditis or pericarditis as defined in the 		

- a. There are no primary immunogenicity objectives in this study.
- b. Seroconversion is defined as an HAI titer <1:10 prior to vaccination and $\ge 1:40$ at the time point of interest, or an HAI titer of $\ge 1:10$ prior to vaccination with at least a 4-fold rise at the time point of interest.

protocol.

c. Seroresponse is defined as achieving a ≥4-fold rise from baseline (before the study vaccination). If the baseline measurement is below the LLOQ, the postvaccination measure of ≥4 × LLOQ is considered seroresponse.

The estimands to evaluate the safety objective are based on the safety population. These estimands estimate vaccine safety after administration of study intervention. Completely missing e-diary data will not be imputed; missing AE dates will be handled according to Pfizer safety rules.

The estimands to evaluate the immunogenicity objectives are based on the evaluable immunogenicity population. These estimands estimate the immune response after study intervention administration in the hypothetical setting where participants follow the study schedules and protocol requirements as directed. Missing immunogenicity results will not be imputed, as MCAR is assumed.

Immunogenicity results that are below the LLOQ will be set to $0.5 \times LLOQ$ in the GMT analyses.

